- IX. Post-operative bleeding complications will be determined using the following data points (see Appendix II):
 - a. Did patient call with concern for post-operative bleeding on the same day of surgery, or post-operative day 0 (POD0)? YES/NO
 - b. Did patient call with concern for post-operative bleeding on POD1? YES/NO
 - c. Did patient call with concern for post-operative bleeding on POD2? YES/NO
 - d. Did patient return to clinic within post-operative days 0-2 for evaluation of post-operative bleeding complication? YES/ NO
 - e. Did patient receive postoperative intervention of any kind for hemorrhagic complication? YES/NO
 - f. Type of intervention performed for bleeding complication.
 - g. Perceived side-effects, if any, by patient due to study intervention.
- X. Study patients will be called 3 days after their surgical procedure to be asked the above data points in case a patient received outside care that was not disclosed to office or research staff.
- XI. Patients' medical charts will be reviewed for and patients will also be asked to divulge the following medical history for demographic and sub analysis purposes (see AppendixIII):
 - a. Age, sex, race
 - b. Medical history including hypertension, coronary vascular disease, liver disease, renal disease
 - c. Medications including anti-platelet agents and anti-coagulants

B. Study duration and number of study visits required of research participants.

- I. Duration sufficient to enroll 124 patients (62 per treatment arm). No additional patient visits will be required beyond the visit normally required for their procedure and/or suture removal.
- II. The initial visit for this study will take place after already scheduled Mohs micrographic surgery which will take no longer than one additional hour during the surgical visit.

- III. Participation includes a total of three days, specifically postoperative days 0-2.
- IV.
- C. Blinding, including justification for blinding or not blinding the trial, if applicable.
 - I. Double-blinded trial in which patients and surgeons will be masked to which treatment arm participants are assigned
- D. Justification of why participants will not receive routine care or will have current therapy stopped.
 - I. Care will be identical in both arms except for addition of topical application of TXA vs normal saline soaked gauze to wound bed at completion of MMS.
- E. Justification for inclusion of a placebo or non-treatment group.

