 - I. There will be a control group of patients who do not receive the intervention, topical TXA, and instead will receive topical application of normal saline in order to provide a blinded comparison to the intervention arm. This will prevent unconscious bias from affecting patient and surgeon perception of postoperative bleeding complications.
- F. Definition of treatment failure or participant removal criteria.
 - I. Patient will be removed from the study if
 - i. Patient removes bandage and cleans wound within 24hrs
 - ii. Patient seeks postoperative care from outside institution within study timeframe (POD0-2), thus not allowing researchers to evaluate postoperative complication. This will be elucidated with a phone call three days after surgery.
 - II. Patients may also voluntarily leave the study. Only patients who complete all steps of the study will be included in data analysis, but the number of enrollees who do not complete the study will be tabulated to track if there is a significant difference between the groups.
- G. Description of what happens to participants receiving therapy when study ends or if a participant's participation in the study ends prematurely.
 - I. There will be no effect on the patient.

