7. STUDY STATISTICS

- A. Primary outcome variable.
 - I. Determination of effects of topical TXA on postoperative hemorrhagic complications and need for additional visits for care related to bleeding complications within the first 2 days following Mohs surgery with a wound allowed to heal by granulation
- B. Secondary outcome variables.
 - I. Determination of possible adverse effects, if any, that are different between the intervention and control arms.
- C. Statistical plan including sample size justification and interim data analysis
 - I. The statistical analysis will be performed by the University of Missouri biostatistics group. The sample size was calculated using a power analysis with the alpha set to 0.05 and the power set to 80%. Dichotomous variables were assessed with an anticipated change of bleeding of 10% in the intervention group and 30% in the control group based on prior clinical experience. No interim data analysis is planned.
 - II. Data will be analyzed on an intention to treat basis.
- D. Early stopping rules.
 - I. Study will end early if severe or high rate of adverse events occur.

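### Removing patients who take off the bandage and clean the wound within 24 hours can delete same-day bleeding events, and the plan contradicts itself on whether such patients are analysed

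*Combined protocol and SAP*

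**What the plan says.** Section 4.F.I.i lists as a ground for removal from the study: "Patient removes bandage and cleans wound within 24hrs". Both acts are required, and the reason for them is not considered. Section 4.F.II sets the consequence: "Only patients who complete all steps of the study will be included in data analysis". Patients who do not complete are counted by arm, but nothing says that their outcomes are used.

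The primary outcome in 7.A.I concerns "postoperative hemorrhagic complications and need for additional visits for care related to bleeding complications within the first 2 days". Section 4.A.IX lists the data points that determine a bleeding complication. The first, IX.a, reads: "Did patient call with concern for post-operative bleeding on the same day of surgery, or post-operative day 0 (POD0)? YES/NO". IX.e adds any postoperative intervention for a hemorrhagic complication. Section 4.A.X provides a telephone call on day 3 that asks the same questions.

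Section 7.C.II states: "Data will be analyzed on an intention to treat basis".

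**The concern.** The removal window (the first 24 hours) falls wholly within the endpoint window (POD0-2). A patient who telephones on the evening of surgery because the wound is bleeding, takes off the bandage and cleans the wound gives a yes on IX.a and also satisfies 4.F.I.i. If 4.F is followed, that patient leaves both the numerator and the denominator.

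Early removal of the bandage happens after randomization, and bleeding can plausibly prompt it. Excluding patients on a possible consequence of the outcome means that the two analysed groups are no longer the groups that were randomized. The planned rates imply only about 25 events in the whole trial (62 × 0.30 + 62 × 0.10 = 18.6 + 6.2 = 24.8), so a handful of lost events matters. Tabulating non-completers, as 4.F.II proposes, would show how many patients left but would not restore their events. With counts this small it would also seldom reveal an imbalance.

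This rule is separate from the outside-care criterion in 4.F.I.ii and applies even to patients who contact only the study clinic.

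**Working it through.** **Inputs from the plan.** Section 7.C.I gives alpha 0.05, power 80% and "anticipated change of bleeding of 10% in the intervention group and 30% in the control group". Section 4.B.I gives 124 patients, 62 per arm. Sidedness is not stated.

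**Reproducing the sample size.** Two-sided test of two proportions, pooled variance under the null, no continuity correction, with p̄ = 0.20:

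n = [1.960·√(2·0.20·0.80) + 0.842·√(0.30·0.70 + 0.10·0.90)]² / 0.20² = (1.109 + 0.461)² / 0.04 ≈ 61.6, so 62 per arm.

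This matches the plan exactly. Power at 62 per arm is 80.3%. Nothing has been added for removals.

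**Assumptions.** The documents do not give q, the share of all POD0-2 bleeding patients who are removed under 4.F.I.i, so I show a range. I take a yes on a bleeding data point as an event, and I assume that no non-bleeding patient is removed, to isolate the outcome-related part.

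**Formulas.** For true rate p in an arm of 62:

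- patients remaining: m = 62(1 − pq)
- observed rate: p(1 − q)/(1 − pq)
- observed odds: p(1 − q)/(1 − p)

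Power uses the same normal approximation with the remaining patients and observed rates.

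**Equal q in both arms.**

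| q | Control | TXA | Risk difference (points) | Risk ratio | Odds ratio | Power |
|---|---|---|---|---|---|---|
| 0 | 30.0% | 10.0% | 20.0 | 0.333 | 0.259 | 80.3% |
| 10% | 27.8% | 9.1% | 18.7 | 0.327 | 0.259 | 76.6% |
| 25% | 24.3% | 7.7% | 16.6 | 0.316 | 0.259 | 69.9% |
| 50% | 17.6% | 5.3% | 12.4 | 0.298 | 0.259 | 54.7% |

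Example at q = 25%: control 0.30·0.75/(1 − 0.075) = 0.225/0.925 = 24.3%; TXA 0.10·0.75/(1 − 0.025) = 0.075/0.975 = 7.7%. Events lost: 18.6 × 0.25 ≈ 4.7 in control and 6.2 × 0.25 ≈ 1.6 on TXA.

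The factor (1 − q) cancels from the odds ratio, which therefore stays at (0.10/0.90)/(0.30/0.70) = 0.259.

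**Unequal q.**

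- 25% of control events lost, none on TXA: 24.3% vs 10.0%, difference 14.3 points, power 55.1%.
- 25% of TXA events lost, none in control: 30.0% vs 7.7%, difference 22.3 points, apparent power 89.4%.

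**How large q could be.** The rule acts only in the first 24 hours. So q is the share of bleeding patients whose bleed falls in that window, times the share of those who both remove the bandage and clean the wound. As illustrations, 50% × 50% gives 25%, and about 71% × 71% is needed to reach 50%.

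**The case against.** The strongest reply is that 7.C.II already promises intention to treat. If it governs, these patients stay in and no event is lost. The root defect would then be the conflict between 4.F.II and 7.C.II, which can be cured without touching the removal criterion. That stands, and it shapes the fix. It does not dispose of the point, because 4.F.II says the opposite in plain terms and nothing ranks the two. A reader might infer that removal simply prevails over the event; the documents do not settle that.

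A reader might also infer that bleeds handled entirely at home are being deleted. The data points are calls, returns to clinic and interventions. A bleed with none of these may meet no data point, so there may be no event to lose. The clear case is the patient who also called or had an intervention.

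The link from bleeding to bandage removal is an inference. The documents do not state it, and the wound-care instructions in Appendix I are not in the supplied text. The rule needs both acts, so changing or reinforcing a dressing without cleaning the wound does not trigger it.

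Finally, it is tempting to say that the rule shrinks the treatment effect. With equal q, only the risk difference shrinks: the odds ratio is unchanged and the risk ratio moves slightly away from 1. The plan names no effect measure. With unequal q, the bias can go either way.

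**Conclusion.** The point holds. Read together, 4.F.I.i and 4.F.II allow primary events to be dropped because of a post-randomization act that bleeding may prompt, and the contrary statement in 7.C.II leaves the primary analysis set undefined for exactly these patients.

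The size is unknown because q is not given. At an equal q of 10% the loss is modest, under 4 points of power. At 25% power is about 70%, and at 50% about 55%; the highest value needs most bleeds to occur within 24 hours and most of those patients to do both acts. Unequal removal is the more serious prospect for interpretation, because it could understate or overstate the benefit.

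The documents do not show that events will be lost, that the bias has a known direction, or that an adherence criterion is wrong in itself. What they show is that the plan permits the loss and contradicts itself about it.

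**What to change.** Reconcile 4.F.I.i and 4.F.II with 7.C.II through an analysis-set rule. State that patients who remove the bandage and clean the wound within 24 hours are classed as non-adherent, remain in follow-up including the day-3 call, and are analysed in the primary comparison as randomized, with IX.a to IX.f scored as observed. The adherence criterion need not be deleted, and no change to wound-care instructions is implied.

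Record the time of early removal and whether bleeding was the reason. Appendix II is not in the supplied text and may already collect this; if it does not, add a field. Run any adherence-restricted analysis only as a sensitivity analysis, dropping only early removals unrelated to bleeding.

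The cost is protocol wording and at most a small form change. The downside is that some patients with less than 24 hours under the dressing stay in the primary analysis, which intention to treat already implies.

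### Patients who seek outside care on POD0-2 are removed from the analysis, although outside care for bleeding is a primary-outcome event and the plan claims intention to treat

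*Combined protocol and SAP*

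**What the plan says.** - Section 4.F.I.ii removes a patient from the study on this ground: "Patient seeks postoperative care from outside institution within study timeframe (POD0-2), thus not allowing researchers to evaluate postoperative complication". The reason for the outside care does not matter, and the removal is triggered by what the day-3 call reveals.
- Section 4.F.II sets the analysis population: "Only patients who complete all steps of the study will be included in data analysis". Non-completers are only counted, to see whether their number differs between groups.
- Section 7.C.II says: "Data will be analyzed on an intention to treat basis".
- Section 7.A defines the primary outcome as hemorrhagic complications and the "need for additional visits for care related to bleeding complications within the first 2 days following Mohs surgery", with no restriction to the study site.
- Section 4.A.X schedules the day-3 call for patients "to be asked the above data points in case a patient received outside care that was not disclosed to office or research staff".
- Among the outcome items in 4.A.IX, item e is not limited by site: "Did patient receive postoperative intervention of any kind for hemorrhagic complication". Item d is limited: "Did patient return to clinic within post-operative days 0-2 for evaluation of post-operative bleeding complication".

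**The concern.** Bleeding treated at another institution on POD0-2 falls within the primary outcome. The day-3 call exists to find it, and items IX.e and IX.f would record it. Section 4.F then takes the patient out of the analysis because of it. The exclusion comes after randomization and can be caused by the outcome itself.

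Two things are at stake. First, if bleeders are removed more readily than non-bleeders, both observed event rates fall and power is lost. If the share removed differs by arm, the estimated effect is biased, and the direction cannot be known in advance. Second, 4.F.II and 7.C.II cannot both be followed. Two analysts who each obey the protocol could report different primary results, and a choice made after unblinding would be open to the charge that the data drove it.

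**Working it through.** **1. The text.** Take a patient who bleeds on POD1, is treated elsewhere, and reports this on the day-3 call.

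| Section | Consequence for this patient |
|---|---|
| 7.A | Has a primary-outcome event |
| 4.A.X, IX.e, IX.f | The event and the type of intervention are recorded |
| 4.F.I.ii | Removed from the study |
| 4.F.II | Not analysed |
| 7.C.II | Analysed in the assigned arm |

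The last two rows contradict each other, and no other passage reconciles them. The heading of 4.F mentions treatment failure, but the text beneath it never scores removed patients as failures or events.

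**2. The plan's own sample size.** Inputs: 30% control and 10% TXA, alpha 0.05, power 80% (7.C.I); 62 per arm (4.B.I). Two-sided testing is assumed, since the protocol does not say. With pooled variance and no continuity correction:

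n = [1.960·√(2·0.20·0.80) + 0.842·√(0.30·0.70 + 0.10·0.90)]² / 0.20² = 61.6, rounded up to 62 per arm.

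The stated figure is reproduced, and it contains no allowance for removals.

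**3. Effect of the removal rule.** Let q be the share of bleeders who go outside and are removed. The documents give no value, so q is an assumption. The observed rate becomes p(1−q)/(1−pq). For example, at q = 20%: control 0.30·0.80/(1−0.06) = 25.5%, TXA 0.10·0.80/(1−0.02) = 8.2%, difference 17.4 points.

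Power is by exact enumeration: 62 randomized per arm, uncorrected Pearson chi-square, two-sided 0.05. The same q applies in both arms.

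| q | Difference (points) | Power |
|---|---|---|
| 0 | 20.0 | 81.0% |
| 5% | 19.4 | 80.1% |
| 10% | 18.7 | 78.5% |
| 20% | 17.4 | 74.3% |
| 33% | 15.3 | 67.5% |
| 50% | 12.4 | 56.5% |

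The normal approximation gives slightly lower powers: 80.3% at q = 0, 76.6% at 10%, 72.3% at 20%.

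**4. Unequal shares.** The true relative risk is 0.10/0.30 = 0.33.

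| q control | q TXA | Observed rates | Relative risk | Power |
|---|---|---|---|---|
| 20% | 10% | 25.5% vs 9.1% | 0.36 | 68.5% |
| 10% | 20% | 27.8% vs 8.2% | 0.29 | 83.2% |

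**5. Type I error.** With a true rate of 20% in both arms, it is 4.7% without removals, 5.1% at equal q of 10% or 20%, 5.2% at 5% vs 10%, and 5.7% at 10% vs 20%. It reaches 12.3% only at 10% vs 40%, an extreme case that is unlikely with blinded patients and surgeons.

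**6. Would the tabulation of non-completers reveal the problem?** Rarely. With 30% vs 10% and q = 20% in both arms, the expected removals are 62·0.30·0.20 = 3.7 and 62·0.10·0.20 = 1.2. The chance of a significant difference is 18%. In the null case with q of 10% vs 20%, it is 7.5%.

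**The case against.** The case for the rule is that staff cannot examine a complication managed elsewhere, so the event would rest on the patient's report. That is a real limitation. But the outcome items are asked by telephone in any case, and an unverified event calls for a sensitivity analysis rather than deletion.

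Several objections to the size of the effect stand as qualifications:

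- **Scale.** With equal q, the odds of an event are multiplied by (1−q) in each arm, so the odds ratio stays at 0.259. The relative risk moves slightly away from 1, from 0.333 to 0.320 at q = 20%. The harm with equal shares is lost power and a smaller absolute difference. Section 7.C names no effect measure.
- **Who is removed.** The rule covers outside postoperative care for any reason. If 10% of bleeders and of non-bleeders alike were removed, the rates would stay at 30% and 10% and power would be 77.5%, which is plain loss of sample size. Falling event rates require bleeders to be removed more often. That is plausible but undocumented.
- **Low q.** At 5 to 10%, the power loss is 1 to 3 points.
- **What counts as an event.** For outside intervention, IX.e is clear. For an outside visit without intervention, event status is inferred from 7.A, because IX.d asks only about return to clinic.

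None of this reconciles 4.F.II with 7.C.II.

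**Conclusion.** The concern holds and must be fixed. The protocol states two incompatible analysis sets for its primary outcome, and one of them discards recorded outcome events after randomization. This follows from the text alone and does not depend on any rate of outside care.

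The numerical consequence does depend on q. It is minor at 5 to 10%, and power drops to 74.3% at 20%. The rows for 33% and 50% show the range and carry no weight in the grading. Inflation of the type I error is not a serious worry unless the shares differ sharply by arm. The documents do not link outside care to the severity of bleeding, so nothing is claimed about which bleeds would be lost.

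**What to change.** 1. Delete 4.F.I.ii as a ground for removal from the analysis.
2. Amend 4.F.II to agree with 7.C.II: all randomized patients are analysed in their assigned arm, and the handling of a missing outcome (for example, a patient not reached on day 3) is stated in advance. The same rule governs patients covered by 4.F.I.i, whose wording should be aligned for the analysis.
3. Count any bleeding-related visit or intervention at any facility on POD0-2 as a primary-outcome event, using the day-3 call.
4. Reword IX.d to cover return to clinic or care at any facility, with the corresponding change to the Appendix II form.
5. Keep patients whose outside care was unrelated to bleeding, as non-events unless a bleeding event is otherwise recorded.
6. Add a sensitivity analysis that counts only events seen at the study site.
7. Keep the tabulation of non-completers by arm as description.

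The cost is a few lines of wording and one extra analysis. The day-3 call is already planned, so no visits, calls or outside record requests are added. The downside is that some events will rest on blinded patient report without clinical verification. Item 6 shows how far the result depends on them.

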5. INCLUSION/ EXCLUSION CRITERIA

- A. Adult (18 years or older) patients being treated with Mohs micrographic surgery will be included in this study.
- B. Surgical procedure must include one of the following:
 - a. Any defect being healed by granulation
 - i. Including periocular defects²²
 - ii. Including defects with fenestrated cartilage^{20,21}
 - iii. Including skin graft donor sites left to heal by granulation
- C. Patients must not

- a. be pregnant or breastfeeding
 - i. urine qualitative pregnancy test will be obtained in-office, prior to surgery, from women of childbearing potential
 - ii. pregnancy test not required on post-menopausal women or women with history of tubal ligation, ablative uterine procedure or salpingo/oophorectomy
- b. Have a known allergic reaction or sensitivity to TXA
- c. Have an international normalized ratio (INR) out of therapeutic range if on warfarin; all patients on warfarin will be tested within one week of surgery
 - i. INR level will be obtained within 1 week prior to time of intervention
 - ii. therapeutic range INR 2.0-3.0
 - iii. if high-risk prosthetic heart valve, therapeutic range INR 2.5 – 3.5

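### Completers-only (4.F.II) and intention-to-treat (7.C.II) rules are not reconciled and no safety set is named, so exposed patients who react and are then removed may drop out of the adverse-effect comparison

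*Combined protocol and SAP*

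**What the plan says.** Two sentences decide who is analysed, and they differ.

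- Section 4.F.II: "Only patients who complete all steps of the study will be included in data analysis". Non-completers are to be counted by arm; nothing is said about analysing their outcomes or side-effects. What counts as completing every step is not defined.
- Section 7.C.II: "Data will be analyzed on an intention to treat basis". The population is not defined and no outcome is named.

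Section 4.F.I gives two grounds for removal:

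- 4.F.I.i: "Patient removes bandage and cleans wound within 24hrs"
- 4.F.I.ii: "Patient seeks postoperative care from outside institution within study timeframe (POD0-2), thus not allowing researchers to evaluate postoperative complication"

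The single secondary outcome, in 7.B.I, is: "Determination of possible adverse effects, if any, that are different between the intervention and control arms". It has no analysis set of its own, and no safety or as-treated population appears anywhere in the document. The data item behind it is 4.A.IX.g: "Perceived side-effects, if any, by patient due to study intervention". Section 4.A.X adds: "Study patients will be called 3 days after their surgical procedure to be asked the above data points". Section 8.A names one drug risk, a local allergic reaction, without a frequency. Section 5.C.b excludes patients who "Have a known allergic reaction or sensitivity to TXA".

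**The concern.** The solution is applied at the end of surgery, and both removal grounds operate after that point. A removed patient has therefore been exposed. Both grounds are also things a patient with a local reaction might do: take off the dressing and wash the wound, or see someone else about it. That link is inference, since the documents give no rate for it, but it means removal may not be independent of the safety outcome.

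If 4.F.II governs and reactors are removed more often than others, the comparison understates reactions in whichever arm causes more of them. A count of non-completers by arm would not reveal this, because it does not show which of them reacted.

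What is at stake is the descriptive safety table. The trial is sized on bleeding, and no test is specified for adverse effects. If the same conflict is raised for the bleeding outcome, this is the safety part of it.

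**Working it through.** **1. The plan's own figure.** Section 4.B.I gives 62 per arm; section 7.C.I gives 30% vs 10% bleeding, alpha 0.05 and 80% power. With a two-sided test, pooled variance and mean rate 0.20:

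n = [1.960·√(2·0.2·0.8) + 0.842·√(0.3·0.7 + 0.1·0.9)]² / 0.2² = (1.109 + 0.461)² / 0.04 ≈ 61.6, so 62 per arm and 124 in total.

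This reproduces the stated size, with no allowance for removals. The figure of 62 is the only trial input used below.

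**2. Tracing patients through the rules.**

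| Patient with a reaction who… | Under 4.F.II | Under 7.C.II |
|---|---|---|
| phones, returns to the study clinic, or reports it at the day-3 call, and meets no removal ground | counted through item g | counted |
| takes the dressing off and washes the wound in the first day | removed, not analysed | stays in |
| goes to another institution on POD0-2 | removed, not analysed | stays in |

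The rules differ only for the last two rows. The plan does not say whether item g is kept for those patients.

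**3. Size if 4.F.II governs.** Let p be the true reaction rate, q the share of reactors removed and r the share of non-reactors removed. All three are assumptions. The rate among completers is

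p(1−q) / [p(1−q) + (1−p)(1−r)].

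This is below p only when q > r; with q = r there is no distortion.

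Difference between arms in percentage points, r = 0:

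| Assumed TXA vs saline | q = 0 | q = 0.25 | q = 0.5 | q = 0.75 |
|---|---|---|---|---|
| 1% vs 0% | 1.00 | 0.75 | 0.50 | 0.25 |
| 2% vs 0% | 2.00 | 1.51 | 1.01 | 0.51 |
| 10% vs 2% | 8.00 | 6.18 | 4.25 | 2.20 |

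Worked cell, 10% vs 2% at q = 0.5: 0.05/(0.05 + 0.90) = 5.26%; 0.01/(0.01 + 0.98) = 1.01%; difference 4.25. If non-reactors are also removed, the same cell becomes 4.69 at r = 0.1 and 5.23 at r = 0.2.

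**4. Chance that no TXA reaction enters the comparison**, (1 − p(1−q))^62:

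- p = 1%: 0.99^62 = 0.536 with no removal; 0.995^62 = 0.733 at q = 0.5.
- p = 2%: 0.98^62 = 0.286 with no removal; 0.99^62 = 0.536 at q = 0.5.

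Expected TXA reactions lost at q = 0.5, out of 62p: 0.31 of 0.62 (1%), 0.62 of 1.24 (2%), 3.1 of 6.2 (10%).

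**5. Would a test change?** Take whole-number counts near the 10% vs 2% case. All treated: 6/62 vs 1/62, Fisher two-sided p = 0.114. Completers, with three TXA reactors removed: 3/59 vs 1/62, p = 0.356. Neither is below 0.05. These counts remove reactors from the TXA arm only, because a single saline reactor cannot be halved. The gap is therefore 5.1% − 1.6% = 3.5 points, rather than the 4.25 of the formula.

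**The case against.** The strongest reply has four parts.

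*It is one contradiction, and it belongs with the primary outcome.* One sentence stating that intention to treat governs would settle most of this, and a separate safety set would then differ only for patients randomised but not treated, or given the wrong solution. This largely stands. Such a sentence would still leave open whether item g is kept for a removed patient, and a repair worded for bleeding alone would leave 7.B.I without a set.

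*The harm needs three unsupported steps.* The completers rule must prevail over the statistical section, a reaction must lead to one of two narrow acts, and reactors must be removed more often than others. All three are needed, and the documents give no data on the last two. This limits the likely size. It does not resolve the conflict, because nothing in the text says that 7.C.II prevails.

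*The plan already has safeguards.* The day-3 call asks about side-effects and is aimed partly at patients who went elsewhere. Non-completers are counted by arm, a severe or high rate of adverse events stops the study (7.D), and problems go to the IRB (8.B.I). The reaction may therefore be recorded, and patient protection does not rest on the disputed set. None of this brings a removed patient's reaction into the comparison of arms. Section 4.F.I.ii uses the same call to find patients to remove, so one conversation could record the reaction and exclude the patient.

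*The rates are invented.* This stands. Known TXA allergy or sensitivity is excluded, so true rates may be low, and at 1% or 2% the expected loss is less than one patient. The 10% vs 2% case has no source and only shows how the formula behaves.

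**Conclusion.** The concern holds. Two current rules give different answers to who enters the adverse-effect comparison, neither yields to the other, and no safety set is named. If 4.F.II is applied as written, exposed patients are excluded for acts that a reaction could prompt.

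The size cannot be determined from the documents. If half of reactors and nobody else were removed, the arm difference would be roughly halved, and at assumed rates of 1-2% on TXA a table with no TXA reaction would become clearly more likely (54% to 73%, and 29% to 54%). The understatement requires that 4.F.II governs and that reactors are removed more often than non-reactors. No test conclusion changes in the case examined. This is a low-severity point about the credibility of the safety table, held with medium confidence.

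**What to change.** Amend 4.F.II and 7.B to state that:

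- adverse effects are compared in every patient to whom study solution was applied, regardless of later removal or completion;
- the completers restriction does not apply to safety;
- the day-3 call is made and item 4.A.IX.g is completed and kept for removed patients, unless they withdraw consent;
- reasons for removal (adverse effect or other) are tabulated by arm.

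The cost is wording only. The call is already planned in 4.A.X and 4.F.I.ii depends on it, so no visits, staff or patients are added. There is a small downside: reported adverse-effect rates may be slightly higher, and some reactions will come from patients whose exposure was cut short.

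### Comparing the number of non-completers between arms cannot show that a completers-only bleeding comparison is unbiased, and the intention-to-treat statement does not say how removed patients' outcomes are handled

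*Combined protocol and SAP*

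**What the plan says.** Section 4.F.I names two reasons for removal after randomization: "Patient removes bandage and cleans wound within 24hrs" and "Patient seeks postoperative care from outside institution within study timeframe (POD0-2), thus not allowing researchers to evaluate postoperative complication". Section 4.F.II adds voluntary withdrawal and sets the analysis population: "Only patients who complete all steps of the study will be included in data analysis". The same sentence gives the check on attrition: "the number of enrollees who do not complete the study will be tabulated to track if there is a significant difference between the groups". It names no test, level, threshold or consequence, and it asks for no table of reasons or outcomes.

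Section 7.C.II states: "Data will be analyzed on an intention to treat basis". Neither section gives a missing-data method or a sensitivity analysis, and no non-completion rate is anticipated anywhere.

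Section 4.A.IX lists the bleeding items (a to e). Section 4.A.X has every study patient telephoned on day 3 and asked those items, so that care received elsewhere comes to light.

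**The concern.** Two things are wrong with using a between-arm comparison of counts to judge attrition. First, at this sample size a moderate imbalance will often not reach significance. Second, the count is the wrong quantity. Bias in a completer comparison depends on how the outcomes of those lost differ from the outcomes of those kept, and equal counts say nothing about that.

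The second point matters here because removal for outside care on days 0 to 2 is close to the endpoint itself, which section 7.A defines as hemorrhagic complications and extra visits for bleeding. A patient who bleeds and goes to another institution is a likely event, and section 4.F takes that patient out of the analysis. What is at stake is how far the primary comparison can be trusted if there is any appreciable loss.

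**Working it through.** **Inputs.** From section 7.C.I: "alpha set to 0.05 and the power set to 80" percent, and "anticipated change of bleeding of 10% in the intervention group and 30% in the control group based on prior clinical experience". From section 4.B.I: "Duration sufficient to enroll 124 patients (62 per treatment arm". Assumed, because the documents are silent: two-sided testing, a 0.05 level for the count comparison, and all non-completion rates.

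**Step 1. Reproduce the planned size.** With pooled variance, no continuity correction and mean rate 0.20:

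n = [1.960·√(2·0.20·0.80) + 0.842·√(0.30·0.70 + 0.10·0.90)]² / 0.20² = (1.109 + 0.461)² / 0.04 = 61.6, so 62 per arm. The plan's figure reproduces. A one-sided test would give 49, which supports the two-sided assumption.

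**Step 2. Power of the count comparison.** For true non-completion rates p1 and p2, sum Bin(a; 62, p1)·Bin(b; 62, p2) over all pairs of counts (a, b) whose test gives p ≤ 0.05.

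| True non-completion | Chi-square | Fisher |
|---|---|---|
| 5% vs 10% | 18% | 9% |
| 10% vs 15% | 13% | 8% |
| 5% vs 15% | 47% | 34% |
| 10% vs 20% | 34% | 26% |
| 15% vs 30% | 52% | 44% |
| 10% vs 25% | 60% | 51% |
| 5% vs 20% | 75% | 65% |
| 10% vs 30% | 81% | 75% |

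In counts: with 3 non-completers in one arm, the other needs 10 (chi-square) or 11 (Fisher) to differ significantly.

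**Step 3. Loss that depends on bleeding equally in both arms.** Let a fraction q of bleeders and 5% of non-bleeders be lost. An arm with bleeding rate p loses L = p·q + (1 − p)·0.05, and its completers bleed at p(1 − q)/(1 − L). For q = 40%:

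- Control: L = 0.12 + 0.035 = 0.155, so 62 × 0.155 = 9.6 lost; completer rate 0.18/0.845 = 21.3%.
- TXA: L = 0.04 + 0.045 = 0.085, so 62 × 0.085 = 5.3 lost; completer rate 0.06/0.915 = 6.6%.
- Difference 14.7 points.

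| q | Expected lost, control vs TXA | Completer difference |
|---|---|---|
| 10% | 4.0 vs 3.4 | 19.4 points |
| 20% | 5.9 vs 4.0 | 18.0 points |
| 30% | 7.8 vs 4.7 | 16.4 points |
| 40% | 9.6 vs 5.3 | 14.7 points |

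At q = 40%, simulated power for the bleeding comparison is about 63%, against 81% with no loss (exact, chi-square). The count comparison flags the imbalance in 22% of trials by chi-square and 15% by Fisher. The odds ratio does not move: (0.30/0.70)/(0.10/0.90) = 3.86 before loss, and (0.18/0.665)/(0.06/0.855) = 3.86 among completers.

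**Step 4. Loss that depends on bleeding differently by arm.** Suppose there is no effect, with 12/62 bleeding in each arm, and six patients leave each arm: all bleeders on TXA, all non-bleeders on control. Completers show 6/56 (10.7%) vs 12/56 (21.4%), a false difference of 10.7 points, while the count comparison gives p = 1.0. This is a constructed extreme, and the false difference is not itself significant (chi-square p = 0.12). It shows only that equal counts carry no information on bias.

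**The case against.** The strongest reply is that section 4.F.II asks only for a tabulation. A reader might infer that a non-significant count will be taken as proof of no bias, or that this check decides whether the result is believed. The documents say neither, and they attach no consequence to the comparison. That reply stands.

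A reader might also call the check the plan's only protection. The documents do not support that either: section 7.C.II states intention to treat, the day-3 call can recover outcomes, and patients and surgeons are blinded. These protections are incomplete, though. The intention-to-treat statement conflicts with section 4.F.II and is silent on missing outcomes. Section 4.F.I uses the day-3 call to identify patients for removal. Blinding does not prevent loss that depends on bleeding in both arms.

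Nor is it right that the check almost never reacts. At 10% vs 30% it flags 75% to 81% of trials.

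The size of the harm rests on assumed loss. At 10% or 20% loss of bleeders the planned difference barely moves. Loss of the same kind in both arms leaves the odds ratio unchanged, shrinks the risk difference towards no effect, and does not inflate false positives (simulated rate 5.1% when both arms bleed at 30%). The plan names no effect measure, so the shrinkage must be described as applying to the risk difference.

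Extreme examples also depend on the test. If full data are 14/62 control vs 11/62 TXA, and five are lost per arm, all bleeders on TXA and none on control, the completers are 14/57 vs 6/57. That gives p = 0.049 by uncorrected chi-square but 0.083 by Fisher, and the plan names no test.

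**Conclusion.** The point holds in a limited form. At 62 per arm and base rates of 5% or 10%, the count comparison has under 50% power for true differences in non-completion of up to about 10 points. Power is roughly even at 15 points and good at 20. At any power, the comparison does not look at outcomes, so neither an equal nor a non-significant count shows that the completer comparison is unbiased. That weakness is material because one removal reason overlaps the endpoint and sections 4.F.II and 7.C.II disagree on who is analysed.

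The direction of bias is not fixed: it can shrink a real difference or create a false one. The non-completion rates, the test and its level are assumptions, and the documents do not establish that any particular bias will occur. This should be corrected before analysis, but it does not invalidate the design.

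**What to change.** 1. Reconcile section 4.F.II with section 7.C.II. The primary comparison should include all randomized patients and count every event known from items IX.a to e and the day-3 call, including events in patients removed under 4.F.I.
2. Replace the significance criterion with a table of non-completers by arm, reason and last known outcome. Do not use a p-value on counts to dismiss attrition.
3. Repeat the primary comparison with unknown outcomes set to (i) no bleeding, (ii) bleeding, (iii) bleeding on TXA only and (iv) bleeding on control only. Report all four with a tipping-point analysis.
4. Do not call a result robust on (i) and (ii) alone; state how far towards (iii) it holds. For example, take 17/57 on control vs 6/57 on TXA with five unknown per arm (uncorrected chi-square throughout). Scenario (i), 17/62 vs 6/62, gives p = 0.011. Scenario (ii), 22/62 vs 11/62, gives p = 0.025. Scenario (iii), 17/62 vs 11/62, gives p = 0.20. A rule resting on (i) and (ii) would certify a result that (iii) overturns.

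The cost is a wording change and four additional two-by-two analyses with a tipping-point report, using data that section 4.A already collects. The downside is that a positive result may have to be reported as sensitive to missing outcomes.
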